In general, permanent discontinuation of study drug refers to premature discontinuation of study drug or completion of study drug and regardless of any gaps in continuous dosing (ie, temporary discontinuation due to adverse event (AE) or subject request after which subjects may resume study drug).

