### 6.2.6. Sensitivity Analyses of the Secondary Efficacy Endpoint While On-Treatment (HIV Infection Rate Ratio Method)

A sensitivity analysis of the secondary endpoint will be based on HIV infections occurring while subjects are on-treatment during the double-blinded phase of the study using the PP analysis set. This on-treatment analysis will include HIV infection events and follow-up times occurring between first dose date to DB phase last dose date plus 10 days (for F/TDF) or plus 16 days (for F/TAF) and exclude:

- 1) HIV-1 infection events and follow-up time during the OLE phase.
- 2) Off study drug PrEP (off-treatment) HIV infection events and follow-up time defined as events and follow-up time occurring greater than 10 days for (F/TDF) or 16 days (for F/TAF) after permanent discontinuation of study drug (Appendix 7).
- 3) HIV infections and follow-up time occurring after subjects initiated any non-study PrEP treatment that includes the period after permanent discontinuation of study drug (including commercial drugs like Truvada®, generic Truvada, or investigational drugs like cabotegravir for PrEP with a stop date that is either ongoing or after permanent discontinuation of study drug).

The HIV infection incidence rate per 100 person-years of follow-up will be computed as the number of subjects with on-treatment HIV infection divided by the sum of all subjects' years (where a year is 365.25 days) of on-treatment follow-up while at risk of HIV infection in study. The duration of on-treatment follow-up while at risk of HIV infection is defined as the time between Day 1 (first dose date) and the end date (end date Day 1 date +1) where end date is defined as:

- For subjects who have been diagnosed as infected with HIV while on-treatment: the date of the on-treatment HIV infection which will be the date of the HIV infection diagnosis (as defined in Section 6.2.2).
- 2) For subjects who have not been infected with HIV while on-treatment, the earlier of:
  - a) last dose date + 10 days for F/TDF or + 16 days for F/TAF for subjects who permanently discontinued study drug (including subjects with off-treatment HIV infection)
  - date of last post-baseline HIV laboratory test (either local or Covance HIV laboratory tests, which may include the 30-day follow-up visit date) for subjects who have not permanently discontinued study drug

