  - start date of any non-study PrEP treatment that includes the period after permanent discontinuation of study drug (including commercial drugs like Truvada, generic Truvada, or investigational drugs like cabotegravir for PrEP with a stop date that is either ongoing or after permanent discontinuation of study drug)
  - d) the first dose date of the OLE phase if available.

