# 27) Toxicity Grades:

- a) For toxicity grade summaries, include all post-baseline graded results up to 30 days after the last dose of study drug, not just those used in by-visit summaries.
- b) For nonfasting glucose, fasting glucose, fasting total cholesterol, fasting triglycerides and fasting LDL grading, as specified in SAP Section 7.2.2.1, the treatment-emergent flag cannot be determined for approximately half of the subjects. As a result, these records will be excluded from the "Maximum Treatment-emergent Toxicity Grade" summary in the "Treatment-emergent Laboratory Abnormalities", Treatment-emergent Grade 2, 3 or 4 Laboratory Abnormalities" or "Treatment-emergent Grade 3 or 4 Laboratory Abnormalities" summary tables. In addition, fasting glucose and nonfasting glucose will be listed as two separate laboratory tests in the "Graded Laboratory Abnormalities" and "Grade 3 or 4 Laboratory Abnormalities" listings. Only a maximum postbaseline toxicity flag will be displayed and the treatment-emergent flag will not be displayed for these tests when the treatment-emergent flag cannot be determined.
- c) Toxicity grades for CD4 will not be displayed in listings. CD4 is scheduled for collection following HIV infection and toxicity grades apply to HIV uninfected subjects.
- 28) Clarification for "Pharmacokinetic Blood Sampling Time Record" listing
  - a) A new variable "Sample age" will be added in this listing, defined as the duration in day between sample collection date and assay date, ie, sample age assay date sample collection date + 1.
  - b) SAMTIME (hours) sample collection time (xx:xx) last dose time before sample collection (xx:xx).
- 28) PK parameters at the individual subject level should be displayed with the following reported number of decimal places:
  - PK concentration data will be reported with 1 decimal place.
- 29) Concomitant nonstudy-drug ARV medications (ie, ARV medications other than study drug that are taken while receiving study drug) will be flagged in "Nonstudy-Drug Antiviral Medication" listing. The logic to define concomitant nonstudy-drug ARV is similar to concomitant non-ARV Medications (see details in Section 7.6.5)

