# b) PEP:

- i) Unknown or blinded medications for PEP: (CMDECOD 'BLINDED INVESTIGATIONAL DRUG' or 'UNKNOWN DRUG') and (CMTRT includes 'PEP' or 'POST EXPOSURE PROPHYLAXIS')
- ii) Include other known ARVs (where CMDECOD not 'BLINDED INVESTIGATIONAL DRUG' or 'UNKNOWN DRUG') excluding the following:
  - (1) F/TDFa 1
  - (2) generic F/TDF
  - (3) HIV vaccine
- iii) For HIV infected subjects, excludes HIV treatments starting on or after the date of HIV diagnosis

At any time that the medication start and end dates of F/TDF (or generic F/TDF) overlaps with the medication start and end dates of another ARV agent (excluding cabotegravir or HIV vaccine) by more than 1 day, that F/TDF (or generic F/TDF) record will be considered as treatment for PEP.

Each ARV agent can be matched to only 1 F/TDF (or generic F/TDF) record.

If the medication start and end dates exactly match between both F/TDF (or generic F/TDF) and another ARV agent, the record will be considered as treatment for PEP, including when the exact match is based on partial medication start and/or end dates of month/year only, year only, completely unknown dates or end date ongoing.

- 36) For the follow up time of HIV infections while on-treatment,
  - a) if the start date of any non-study PrEP treatment that includes the period after permanent discontinuation of study drug is incomplete, such instances should be queried. If incomplete start dates remain after query, the first of the month should be used for the start date of the non-study PrEP medication when determining on-treatment HIV infection events or on-treatment follow-up time.
  - b) if any non-study F/TDF for PrEP treatment that includes the period after permanent discontinuation of study drug overlaps with a 3rd ARV agent, the start date of non-study PrEP treatment will be used unless the start date of the 3rd ARV agent and non-study F/TDF is the same in which case the end date + 1 day of the 3rd ARV agent will be used as the start date for non-study F/TDF for PrEP treatment. Incomplete start and end dates should be queried. If incomplete end dates of the 3rd agent remain after query, the last day of the month should be used for the start date of the non-study PrEP medication when determining on-treatment HIV infection events or on-treatment follow-up time.

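### In the on-treatment HIV analysis, a non-study PrEP course that starts and stops before permanent discontinuation of study drug stays in the assigned arm's events and person-time; a longer course is censored from its start

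*SAP*

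**What the plan says.** SAP 6.2.6 describes a per-protocol, on-treatment sensitivity analysis of the end-of-blinded-phase HIV endpoint. Follow-up runs from first dose to the last blinded dose plus 10 days (F/TDF) or 16 days (F/TAF). Exclusion 3 removes "HIV infections and follow-up time occurring after subjects initiated any non-study PrEP treatment that includes the period after permanent discontinuation of study drug". End-date rule 2(c) censors uninfected participants at the "start date of any non-study PrEP treatment that includes the period after permanent discontinuation of study drug". Both are limited to courses "with a stop date that is either ongoing or after permanent discontinuation of study drug".

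Appendix 12 item 36, which programs this follow-up time, carries the same limit: "if the start date of any non-study PrEP treatment that includes the period after permanent discontinuation of study drug is incomplete".

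SAP section 3 defines permanent discontinuation "regardless of any gaps in continuous dosing". SAP 4.2.2 expects drug holidays and other interruptions before that point.

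Appendix 12 item 35(a) recognises as PrEP only cabotegravir, F/TDF or generic F/TDF, and certain blinded or unknown records labelled as PrEP. Item 35(b)(ii), on PEP, says "Include other known ARVs" and excepts only F/TDF, generic F/TDF and HIV vaccine. SAP 7.6.4 excepts F/TDF, cabotegravir and HIV vaccine. Item 29 flags in a listing "ARV medications other than study drug that are taken while receiving study drug".

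**The concern.** This is the only specified analysis that tries to remove non-study PrEP; the FAS analysis does not. A reader will take its rates as those seen under the assigned drug. Under the present rule two participants with the same start date and the same non-study F/TDF are handled differently because one course stopped just before the last study dose and the other just after. The first keeps all infections and follow-up in the assigned arm. The second loses everything from the start of the course.

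In the F/TAF arm the retained drug is the comparator, so part of what is reported as F/TAF experience is F/TDF experience. The on-treatment rates also appear in Appendix Table 5, where each arm is set against a predicted incidence without PrEP and the other arm offers no offset.

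**Working it through.** **Does another rule catch a nested course?**

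- *Per-protocol set (SAP 3.1.3).* The only medication exclusion is ongoing therapy with drugs in protocol Table 5-1, which names no PrEP drug or other antiretroviral.
- *Adherence.* SAP 6.3 drops the protocol's non-adherence exclusion from this set.
- *Dosing gaps.* A gap does not end on-treatment time, because permanent discontinuation ignores gaps.
- *Non-study ARVs.* SAP 7.6.1 and Appendix 12 item 29 list and flag them, with no analysis.
- *PEP summaries (SAP 7.6.4).* F/TDF is outside the PEP definition.

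None does. A course that starts and stops before permanent discontinuation is retained.

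**The coding lists.** Non-study F/TAF is not among the PrEP drugs in item 35(a). As a known ARV it falls into PEP under 35(b)(ii). Cabotegravir is PrEP under 35(a). When it is recorded as a non-Gilead investigational drug it also meets 35(b)(ii), contrary to 7.6.4.

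**The plan's power figure.** Inputs from protocol 8.8: 2500 per arm, 2 years' average follow-up, 1.44 per 100 PY in both arms, margin 1.62, two-sided 5%.

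- Events per arm: 2500 × 2 × 0.0144 = 72.
- SE of the log rate ratio: √(1/72 + 1/72) = 0.1667.
- Power: Φ(ln 1.62 / 0.1667 − 1.96) = 82.5%, which agrees with the stated minimum of 82%.

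**Illustrative size.** Let f be the share of F/TAF person-time covered by nested non-study F/TDF. This share is assumed; the documents give none. Assume also that covered time has the F/TDF rate and that the F/TDF arm is unaffected. A true ratio of 1.62 is then seen as 1.62(1 − f) + f. The false non-inferiority column is the chance of declaring non-inferiority when the true ratio is 1.62. The last column is power at equal rates if only the covered F/TAF time is excluded. The planned 5000 PY per arm stands in for on-treatment time.

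| f | Ratio seen | One-sided false non-inferiority | Power after exclusion |
|---|---|---|---|
| 0 | 1.620 | 2.5% | 82.5% |
| 0.5% | 1.617 | 2.6% | 82.4% |
| 1% | 1.614 | 2.7% | 82.3% |
| 2% | 1.608 | 2.8% | 82.1% |
| 5% | 1.589 | 3.4% | 81.5% |
| 10% | 1.558 | 4.4% | 80.4% |

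Example at f = 5%: 1.62 × 0.95 + 0.05 = 1.589. Excluding 5% of F/TAF time leaves 72 × 0.95 = 68.4 expected events in that arm, SE √(1/68.4 + 1/72) = 0.1688, power 81.5%. If both arms lost 5%, SE would be √(2/68.4) = 0.1710 and power 80.5%.

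**The case against.** **The rule already removes much of this use.** A course begun on study drug that is ongoing or outlasts it is censored from its start. This stands: a reader might infer that all non-study PrEP taken on study drug is credited to F/TAF, and the text does not support that. Only nested courses remain.

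**The direction is not shown.** The rule is identical in both arms. F/TDF taken in gaps in the F/TDF arm lowers that arm's rate and raises the ratio, and infections during nested courses still count against the arm. For F/TDF taken on top of F/TAF with no gap, no document gives a rate. This stands too, so a claim of bias in favour of non-inferiority goes beyond the documents.

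**Negative person-time.** A reader might infer it when a course began before first dose and is recorded as ongoing. But 6.2.6 confines follow-up to time from first dose, and nothing suggests such records exist. It is an edge case a programmer would probably catch; stating a Day 1 floor settles it.

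**Commercial F/TAF.** A reader might infer that it can never censor. That is too strong, since 6.2.6 and item 36 speak of any non-study PrEP. The conflict is with the list in item 35. In the F/TAF arm it is also the assigned drug.

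**Table 5-1 bars other agents with significant nephrotoxic potential.** This does not plausibly cover the trial's own comparator.

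**It is a sensitivity analysis.** Non-inferiority on the secondary endpoint is concluded from the FAS. This limits the importance of the point but does not remove the inconsistency.

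**Conclusion.** The definition should be corrected. Retaining or removing the same non-study PrEP according to its stop date has no rationale in the SAP, and no other rule closes the gap. The net effect on the rate ratio has no fixed sign, and its size cannot be known from the documents. The F/TAF-arm component alone moves a true 1.62 to 1.61, 1.59 or 1.56 at 2%, 5% or 10% coverage. Those figures rest on an assumed extent, on the F/TDF rate applying in covered time, and on no offset from the F/TDF arm. At about 1% or less the effect is negligible. The point concerns a sensitivity analysis and does not touch the FAS conclusion.

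**What to change.** 1. In SAP 6.2.6 exclusion 3, end-date rule 2(c) and Appendix 12 item 36, delete the clause limiting the rule to courses that reach past permanent discontinuation, together with the linked stop-date condition.
2. Exclude person-time, and infections diagnosed, during any non-study PrEP course that overlaps on-treatment follow-up, counting only time from Day 1. Interval exclusion is preferable to permanent censoring, which would discard all later on-drug follow-up after even a short course.
3. In item 35(a), add non-study F/TAF without a third agent to the PrEP list, and amend 7.6.4 so that it is excluded from PEP. In item 35(b), exclude cabotegravir from PEP, as 7.6.4 already does.
4. Report by arm the participants and person-years affected. Show the result under the rule as now written alongside, because the study was already unblinded for the primary analysis.

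The cost is SAP wording and reprogramming on dates already collected, plus a small loss of person-time. At an assumed 5% coverage, power goes from 82.5% to about 81.5% if only F/TAF time is lost, or 80.5% if both arms lose 5%.

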### 6.2.7. Subgroup Analysis of the Secondary Efficacy Endpoint

The analysis of the incidence of HIV-1 infection rate per 100 PY will be performed within each subgroup specified in Section 3.4 based on the FAS (Appendix 2).

For each level of the subgroup factors, the incidence rates within each treatment group and 95% CIs will be computed using the exact CIs for the single Poisson rate parameter approach as described for the rate differences method in Section 6.2.8.1.

### 6.2.8. Exploratory Analysis of the Secondary Efficacy Endpoint

### 6.3. Changes From Protocol-Specified Efficacy Analyses

The adherence criteria (excluding non-adherent to study drug subjects) is not required for the PP analysis set. For HIV prevention, a lower adherence rate is associated with an increased risk of HIV infection events and thus increased statistical power for evaluation of the HIV infection rate.

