8.2.1.3. Per Protocol (PP) Analysis Set

The PP analysis set will include all participants who (1) randomize into the study, (2) receive at least one dose of study drug, and (3) have not committed any major protocol violation, including the violation of key entry criteria.

Participants meeting any of the following criteria will be excluded from the PP analysis set:

- HIV-1-positive at baseline
- Participants who meet the exclusion criterion for receiving ongoing therapy with any of the medications listed in the table in protocol Section 5.4 including drugs not to be used with FTC and TAF
- Nonadherence to study drug: participants with poor adherence rate for active study drug

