## 3.1.3. Per Protocol Analysis Set

The **Per Protocol (PP) Analysis Set** will consist of all subjects in the FAS excluding those with any of the major protocol violations listed below. Subjects will be grouped according to the treatment they actually received. The PP analysis set will be used for an on study drug PrEP treatment (on-treatment) HIV infection sensitivity analyses of the primary endpoint.

PP analysis set will exclude (from FAS) subjects meeting any of the following criteria:

- Subjects where evidence suggests that they have pre-existing HIV that was contracted prior
  to first dose date of study drug (defined as subjects for whom HIV infection prior to first
  dose date of study drug cannot be excluded as the subjects did not have a Covance HIV
  antibody or HIV-1 RNA test analyzed between first dose date (inclusive) and prior to the
  date of diagnosis of HIV infection) based on Gilead's evaluation
- Subjects vaccinated for HIV (identified from the Medical History eCRF or Non-Study ARV Medication eCRF)
- Subjects who meet the exclusion criterion for receiving ongoing therapy with any of the medications listed in the table in protocol Section 5.4 including drugs not to be used with FTC and TAF

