# 3.8. Analysis Windows

# 3.8.1. Definition of Study Day

**Study Day 1 (DB phase)** is defined as the day when the first dose of randomized study drug (ie, *F/TAF or Placebo-to-match F/TAF*, *F/TDF or Placebo-to-match F/TDF*) was taken, as recorded on the Study Drug Administration eCRF form.

**Study Day 1 (OLE phase).** For subjects who were treated in the OLE phase, Study Day 1 is defined as the day when the first dose of OLE phase study drug (ie, F/TAF) was taken, as recorded on the "Extension Phase" Study Drug Administration eCRF.

**Study Days** are calculated relative to Study Day 1 for each phase. For events that occurred on or after the Study Day 1 date, the number of study days is calculated as (visit date minus Study Day 1 date plus 1). For events that occurred prior to DB phase Study Day 1, the number of study days is calculated as (visit date minus Study Day 1 date).

**Last Dose Date (DB phase)** is the latest of the blinded study drug end dates (administering ≥1 tablet per day) recorded on the Study Drug Administration eCRF form with "Permanently Withdrawn" box checked for subjects who prematurely discontinued or completed study drug in the blinded treatment study phase according to the Study Drug Completion eCRF.

If last dose date is completely missing (ie, due to lost to follow-up) for subjects who prematurely discontinued or completed blinded study drug at the data cut date in the DB phase, the latest of study drug start dates and end dates, the clinic visit dates, and the laboratory visit dates excluding the date of 30-day follow-up visit, from the DB phase data, will be used to impute the DB phase last dose date. For other partial missing last dose date, please see the programming specifications for imputation rule details.

If the DB phase last dose date is after the first dose date of the OLE phase, use the day before the first dose date of the OLE phase to impute it.

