# 4.3. Protocol Deviations

A summary will present the number and percentage of subjects who did not meet at least 1 eligibility criterion and the number of subjects who did not meet specific criteria by treatment group and overall based on the Safety Analysis Set. A by-subject listing will be provided for all randomized subjects who violated at least 1 inclusion or exclusion criterion. The listing will include the criteria not met. A listing of subjects who received the wrong study drug will also be provided.

Protocol deviations occurring after subjects entered the study are documented during routine monitoring. The number and percentage of subjects with important protocol deviations by deviation reason and the total number of important protocol deviations by deviation reason (ie, nonadherence to study drug, violation of select inclusion/exclusion criteria) will be summarized by treatment group for the Full Analysis Set. A by-subject listing will be provided for those subjects with important protocol deviation.

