## 6.2.5. Primary Analysis of the Secondary Efficacy Endpoint (HIV Infection Rate Ratio Method)

The analysis purpose of the secondary efficacy endpoint is to assess the noninferiority of treatment with F/TAF relative to treatment with F/TDF via HIV infection rate ratio estimation from a Poisson regression model. Noninferiority will be assessed using a 95% CI constructed using a generalized model associated with a Poisson distribution and logarithmic link with the treatment group being the main effect and a noninferiority margin of 1.62.

It will be concluded that F/TAF is noninferior to F/TDF if the upper bound of the 2-sided 95% CI of the rate ratio (F/TAF group over F/TDF group) of the HIV infection incidence rate is less than 1.62 (Appendix 2).

If noninferiority of F/TAF versus F/TDF is established, the same 95% CI used in evaluating noninferiority will be used to evaluate superiority. If the upper bound of the 95% CI is less than 1, then superiority of F/TAF over F/TDF using the rate ratio estimation is established. The p-value from a Poisson model will also be used to assess superiority as a secondary assessment. The FAS will be used for the secondary efficacy endpoint analysis and the superiority evaluation.

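### Does dropping the poor-adherence exclusion from the per-protocol set, on grounds of power alone, call for a change to the plan?

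*SAP*

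**What the plan says.** Protocol section 8.2.1.3 lists among its PP exclusions "Nonadherence to study drug: participants with poor adherence rate for active study drug". It does not say what counts as poor.

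SAP section 6.3 declares the departure openly: "The adherence criteria (excluding non-adherent to study drug subjects) is not required for the PP analysis set". Its only reason is that "a lower adherence rate is associated with an increased risk of HIV infection events and thus increased statistical power".

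The roles of the two sets are stated elsewhere in the SAP:

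- Section 6.2.5: "The FAS will be used for the secondary efficacy endpoint analysis and the superiority evaluation".
- Section 3.1.3: "The PP analysis set will be used for an on study drug PrEP treatment (on-treatment) HIV infection sensitivity analyses of the primary endpoint".
- Section 3.1.2, which defines the FAS, has no adherence condition.

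Section 6.2.6 sets out the PP on-treatment analysis. It removes time more than 10 days (F/TDF) or 16 days (F/TAF) after permanent discontinuation, and time after non-study PrEP is started. It gives rates and follow-up rules but no non-inferiority criterion.

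**The concern.** Infections in people taking little of either drug say little about which drug protects better. If the share of such people and their risk are similar in the two arms, their infections move a ratio above 1 toward 1, which makes non-inferiority easier to conclude. Section 6.3 mentions only the gain in events.

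The on-treatment rule does not remove this group. Under SAP section 3.8.1 the last dose date depends on the withdrawal "box checked for subjects who prematurely discontinued or completed study drug in the blinded treatment study phase", and SAP section 3 treats permanent discontinuation "regardless of any gaps in continuous dosing". Someone who rarely takes tablets but is never formally stopped therefore stays in. SAP section 4.3 tabulates deviations such as "nonadherence to study drug, violation of select inclusion/exclusion criteria" by arm, but the visible text links them to no rate ratio.

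At stake is whether the PP analysis works as a check on dilution by poor adherence during nominal treatment.

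**Working it through.** **1. The plan's power figure.** Inputs from Protocol section 8.8: 2500 per arm, 2 years' average follow-up, 1.44 per 100 PY in both arms, margin 1.62, two-sided 5%.

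- Person-years per arm: 2500 × 2 = 5000. Events per arm: 5000 × 0.0144 = 72.
- SE of the log ratio: √(2/72) = 0.1667.
- Power: Φ(ln 1.62/0.1667 − 1.96) = Φ(0.93) = 82.5%, against a stated figure of at least 82%.

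**2. The reason in section 6.3.** At a true ratio of 1, removing 25%, 50% or 75% of the 72 events leaves 54, 36 or 18 per arm. The same formula gives power of 71%, 54% or 30%. The reason is correct at that ratio.

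**3. The effect section 6.3 omits.** Assume 72 F/TDF events, an on-drug ratio of 1.62, a ratio of 1 in non-takers, and a fraction f of control events in non-takers. Then e₂ = 72, e₁ = 72 × [f + (1 − f) × 1.62], and the chance that the upper limit is below 1.62 is Φ((ln 1.62 − ln(e₁/e₂))/√(1/e₁ + 1/e₂) − 1.96).

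| f | Blended ratio | Chance of passing |
|---|---|---|
| 0 | 1.62 | 2.5% |
| 25% | 1.47 | 9.6% |
| 50% | 1.31 | 27% |
| 75% | 1.16 | 56% |

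At f = 50%, a non-taker ratio of 0.7 or 1.3 instead of 1 changes 27% to 55% or 10%.

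A second set-up uses shares of person-time. Let 10% be at the equal-weighted placebo rate of 6.96 per 100 PY (Protocol Table 8-1) in both arms. F/TDF: 0.9 × 1.44 + 0.1 × 6.96 = 1.992. F/TAF: 0.9 × 1.44 × 1.62 + 0.1 × 6.96 = 2.796. The ratio is 1.40 and the chance of passing is 19%. With 4.70 per 100 PY (SAP Appendix Table 10, lowest band) they are 1.46 and 12%.

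The mechanism is real. The shares are assumptions, because the documents give none for this trial.

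**4. Where those chances apply.** They use the 1.62 rule on full-trial events, and that rule belongs to the FAS. The FAS has no adherence condition, so section 6.3 changes none of them.

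**5. Whether an adherence-restricted ratio would help.** The ready-made cut-offs are the pill-count bands in SAP section 4.2.3.1. Expected tablets there run from first dose to the latest dosing, clinic or laboratory date. For infected participants the end is the later of diagnosis and last dose. Protocol sections 3.2 and 6.9 let participants stop drug and keep attending, and ask sites to retain them. Compare two people who take every dose to Week 48 (336 days) and then stop:

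- Uninfected, attends to Week 96: 336/672 = 50%. A cut at 60% removes this person.
- Diagnosed at Week 48: 336/336 = 100%. This person is kept.

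Both were fully adherent while on drug. Keeping the case and deleting the comparable uninfected person-time makes selection depend on outcome. The ratio then shifts as far as the arms differ in stopping while still attending.

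**6. Precision.** At an observed ratio of 1, an upper limit below 1.62 needs 2/(ln 1.62/1.96)² = 33.01 events per arm, so 34. With 10 or 20 per arm the interval is 0.42 to 2.40 or 0.54 to 1.86. In the two highest bands of Appendix Table 10 (a different cohort) there were 0 infections in 316 + 181 = 497 PY. The exact upper 97.5% bound is 3.689/497 = 0.742 per 100 PY, or 37 events in 5000 PY. Good adherers might thus supply anything from 0 to 37 events per arm before any person-time is removed.

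**7. What else the SAP examines.**

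- Appendix 9 has a dried-blood-spot cohort describing adherence by arm and a case-control substudy relating drug level to infection within each arm.
- Appendix 8 and Appendix Table 5 compare each arm, for both the FAS and the PP on-treatment analysis, with a predicted rate without PrEP.
- Appendices 6 and 12 show a rate-difference method, with a margin of 1.2 per 100 PY in Appendix 6. In the second set-up the difference shrinks only from 0.893 to 0.804, the factor 1 − f.

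**The case for a change.** The strongest case is that the SAP already accepts dilution by poor adherence elsewhere. Section 1.3.1 warns that incomplete adherence will shrink the BMD and renal differences, where it works against the hoped-for result. For HIV it can work in favour of a non-inferiority claim, and section 6.3 does not say so. In Appendix Table 10, 18 + 9 = 27 of 28 infections fell in the two lowest drug-level bands. None of the analyses listed under item 7 gives a between-arm ratio among people who took the drug. One balancing sentence and one descriptive table would cost little.

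The description stands: the rationale is one-sided, and no visible analysis gives that ratio. Section 6.2.8 has no text in the public copy and the Primary Analysis SAP is not available, so a related analysis cannot be ruled out.

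The remedies do not follow from this. The pill-count table fails on its denominator (item 5). Unreturned bottles also count as taken, so some non-takers would remain. With no protocol threshold, any cut-off would be a new post-randomisation rule set after the unblinding for the primary analysis (SAP section 1). A row based on the section 4.3 nonadherence deviation avoids a new cut-off, but the documents do not define that deviation. The extra sentence would be accurate and would change no number or conclusion.

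**Conclusion.** No change is needed. Section 6.3 gives one of two effects, and the effect it gives is correct at a true ratio of 1. The omitted effect could be large under assumed conditions: with half the control events in non-takers and an on-drug ratio of 1.62, the blended ratio is 1.31 and the chance of passing is 27%. That applies to the FAS analysis, which section 6.3 does not alter, and it requires similar low-drug risk and similar low-adherence shares in the two arms. Imbalance could move the ratio either way.

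Leaving out a post-randomisation exclusion that had no threshold is a fair trade-off in a sensitivity analysis, and it was declared. The available substitute would select on outcome and could leave too few events to exclude 1.62. If a restricted ratio were ever reported, adherence would have to be measured from first to last dose in the same way for infected and uninfected participants, and the result would be exploratory. The conclusion rests on the FAS remaining the deciding set and on section 6.2.6 carrying no decision rule, as the SAP now reads.
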